2 BACKGROUND

Hypoglycemia elicits a multifaceted hormonal response that helps restore glycemic levels to normal. As blood glucose levels start to fall, insulin secretion ceases. At the top of this hierarchy of counterregulatory responses are glucagon and epinephrine which are the two principal hormones that act rapidly to increase glucose production and inhibit glucose utilization to raise plasma glucose levels back to normal¹. In cases of prolonged and/or more severe hypoglycemia, growth hormone and cortisol are mobilized to stimulate the synthesis of gluconeogenic enzymes and inhibit glucose utilization². In non-diabetic individuals, glucagon and epinephrine are usually very effective and the latter responses are rarely required in the acute situation. In contrast, impaired glucose counterregulation presents itself in longstanding diabetes and with antecedent hypoglycemia³. Within the first five years after the onset of Type 1 diabetes (T1DM), the primary defense against hypoglycemia, the release of glucagon, either becomes significantly attenuated or is completely absent in diabetic patients and this impairment appears to be specific for the stimulus of hypoglycemia^{4,5}. Hence, patients with diabetes primarily depend on the release of epinephrine as their main defense against hypoglycemia. Unfortunately, with longer duration of diabetes and especially with poor glycemic control, epinephrine secretion is also compromised, making these patients even more vulnerable to the threat of hypoglycemia⁵⁻⁷. In patients with diabetes, hypoglycemia arises from the interplay of a relative excess of exogenous insulin and defective glucose counterregulation and it remains a limiting factor in attaining proper glycemic management. Both the Diabetes Control and Complications Trial (DCCT) conducted in Type 1 patients⁸ and the United Kingdom Prospective Diabetes Study (UKPDS) conducted in Type 2 patients⁹, have established the importance of maintaining good glucose control over a lifetime of diabetes to avoid cardiovascular, renal and neurological complications. However, lowering glycemic goals for diabetic patients increases their risk for hypoglycemia exposure. According to the DCCT, T1DM patients put on intensive insulin therapy, though having improved outcomes for diabetic complications, are at a 3-fold higher risk of experiencing severe hypoglycemia compared to those on conventional insulin therapy¹⁰. Moreover, recent antecedent hypoglycemia reduces autonomic (epinephrine) and symptomatic (which normally

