4 STUDY DESIGN

4.1 Description

The current study will be a double-blinded, placebo-controlled study in which Type 1 diabetic patients with hypoglycemia unawareness are randomized to either 1) placebo treatment, 2) 2.5mg carvedilol twice daily or 3) 3.125mg carvedilol twice daily. After enrollment, the participants will be placed on (blinded) CGM monitoring which will be continued until the end of the study. Additionally, participants will be provided with a glucometer to measure their blood glucose and for calibrating the CGMs during the study. One week after CGM placement, the participants will undergo the first hypoglycemic clamp study to obtain baseline measures of hypoglycemia frequency (from downloaded CGM data), hypoglycemia awareness scores and hormone responses. Following the initial clamp procedure, the patients will be randomized to either 4 weeks use of carvedilol or placebo. After the 4 weeks of treatment, the participants will undergo a second hypoglycemic clamp session. Patients will be hospitalized the night before each clamp study to ensure stable glucose levels.

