collected to measure glucose, HbA1c, hematocrit and hormones (glucagon, catecholamines, insulin, cortisol, growth hormone, pancreatic polypeptide). Blood samples collected for assessment of plasma glucose (1mL) during the clamping procedure will be aliquoted into heparin coated 1ml Eppendorf tubes to prevent coagulation and processed immediately in the YSI and/or Analox Instruments glucose analyzer. In addition, the participants will be asked to fill in questionnaires to assess their perception of hypoglycemic symptoms (Edinburgh Hypoglycemia Symptom Scale) and their fear of hypoglycemia. Subsequently, the subjects will be given KCl tablets (20-40mEq) to help maintain potassium levels during the clamping procedure. Once assessment of baseline parameters has been completed, constant insulin (2mU/kg/min) and variable 20% dextrose infusions will be started at -60 minutes to establish stable glucose levels of ~90mg/dl before gradually lowering plasma glucose levels in three steps from 90-65-55-45 mg/dl by gradually reducing the glucose infusion rate. Plasma glucose levels will be monitored from a 1ml blood sample every 5min using a YSI and/or Analox glucose analyzer. A second Analox Instruments glucose analyzer and glucometer will be kept on hand as a backup. It is important that the glucose levels NOT be communicated verbally during the clamping procedure as notification of declining glucose concentrations to the participant might trigger confounding (i.e. artificially higher) awareness scores or stress hormone responses. Each glycemic step will be held for 30 minutes, allowing enough time for blood collection (~30mL at each glycemic plateau) and completion of the Edinburgh questionnaire at each glycemic plateau. At each glycemic step, plasma hormones (glucagon, catecholamines, insulin, cortisol, growth hormone, pancreatic polypeptide) will be evaluated. The frequent assessment of hypoglycemia symptom scores allows us to identify the threshold at which hypoglycemic symptoms are first noticed by the subject. We chose glycemic targets of 55 and 45mg/dl as hypoglycemic symptoms generally first appear between 55-65mg/dl in hypoglycemia aware individuals. In contrast, symptoms may not manifest in hypoglycemia unaware patients until glucose levels reach 45mg/dl. Targets of 55 and 45mg/dl allow us to safely determine whether carvedilol treatment raises the glucose threshold at which symptoms are first detected (i.e. improving hypoglycemia awareness). No more than 500mL of blood will be collected throughout the entire clamping procedure which is equivalent to the volume of a single blood donation. After the clamp, the participant's glucose levels will be recovered to normal by stopping the insulin infusion and raising the glucose infusion rate. In addition, a meal will be provided to aid recovery. This first set of clamps will establish a baseline response in the participant prior to the start of the intervention phase of the study. **Dispersal of Intervention Drug:** At the end of the clamp procedure, the subjects will be supplied with either placebo or one of two different doses of carvedilol, 2.5mg or 3.125mg, along with instructions on how to take the medication. The research staff and participant will be blinded to the treatment being received. The initial dose will be taken on the day following the clamp. In addition, the participant will also receive a hypoglycemia log book along with instructions on how to document hypoglycemia incidences and whom to contact in case of medical concerns. Once the participant's blood glucose levels are stable and he/she is ready to be discharged, we will provide them with glucose tablets and we will cover the cost of transportation home as a precautionary measure.

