
Follow-Up Visit: About 7-14 days after the start of the intervention phase, the subjects will be asked to come into the clinic for a follow-up visit where vital signs, AE and CGM data will be monitored or evaluated. Subjects will also be asked to complete a hypoglycemia awareness and fear survey at this time.

Second Hypoglycemic Clamp: At the end of the four-week intervention phase, the subjects will return to the CSC for the overnight stay and second hypoglycemic clamp procedure. The second hypoglycemic clamp procedure will be identical to the first described above.

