9.11.1 Primary Objective Assessment

The primary objective assessments are 1) improvements in the hypoglycemia symptom scores at each of the (hypoglycemic) glycemic plateaus, 2) shift in the threshold for the detection of hypoglycemia and 3) whether counterregulatory hormone responses improve during the second hypoglycemic clamp in T1DM patients with impaired awareness of hypoglycemia after 4 weeks of carvedilol treatment compared to their baseline and/or compared to the placebo-treated control group.

The symptom scores will be assessed by the Edinburgh Hypoglycemia Symptom Score. Results will be kept in the patients CRF. After the study is complete, the results will be loaded into a secure electronic database and analysis will begin. When reporting the results of the hypoglycemia symptom scores, we will evaluate individual as well as overall or total symptom scores. In addition, symptoms will be grouped into autonomous, neuroglycopenic and other symptoms for evaluation.

The counterregulatory hormone responses (glucagon, epinephrine, norepinephrine, cortisol and growth hormone) will be analyzed from the drawn blood samples. Whole blood samples will be collected and aliquoted into vacutainers containing the appropriate preservatives and anticoagulants, spun down and the plasma portion will be stored in a -80°C freezer until the samples are analyzed.

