10 STATISTICAL CONSIDERATIONS

A total of 21 T1DM patients with impaired awareness of hypoglycemia will be sought for this study. For the dose response study, we plan to enroll 21 of these patients who will be randomized to either placebo (N=7) or carvedilol (2.5mg or 3.125mg twice daily; N=7 each).

In estimating the appropriate sample sizes required to yield adequate statistical power, assuming a Type II error rate (β) of no more than 20% for a given test and a Type I error rate of $\alpha=5\%$, we used the following: $\text{Power} \geq 1-\beta = 1-0.2 = 0.8$

Treatment effects will be analyzed using one- or two-way analysis of variance (ANOVA) for independent or repeated measures as appropriate, followed by suitable *post-hoc* analysis. Analyses will be performed using the GraphPad Prism[®] or SAS[®] suite of software. We will use a significance level of $\alpha<0.05$.

Primary variables:

- a) Symptom Scores (autonomous, neuroglycopenic and other symptoms of hypoglycemia)
- b) Counterregulatory Hormone Responses (glucagon, epinephrine, norepinephrine, growth hormone and cortisol levels)

Secondary variables:

- a) Frequency of hypoglycemia assessed by CGM.

The primary and secondary variables will be analyzed by the statistical approaches mentioned above.

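### The primary analysis does not say how the pre-randomization clamp enters the comparison of arms, and Section 9.11.1 lets an uncontrolled change from own baseline count as improvement

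*Combined protocol and SAP*

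**What the plan says.** Section 10 and the Statistical Methodology row of the Study Summary carry the same sentence: "Treatment effects will be analyzed using one- or two-way analysis of variance (ANOVA) for independent or repeated measures as appropriate", followed by a post-hoc analysis that is not named. Neither place gives a covariate, the term to be tested, or whether the repeated factor is clamp or glycemic plateau.

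The design supplies a clean baseline. Section 4.1: "Following the initial clamp procedure, the patients will be randomized to either 4 weeks use of carvedilol or placebo". Section 9.10 says of the first clamp: "This first set of clamps will establish a baseline response in the participant", and of the second: "The second hypoglycemic clamp procedure will be identical to the first described above". So every participant has the same measurements at the same plateaus before and after treatment.

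Section 9.11.1 sets as primary assessments "improvements in the hypoglycemia symptom scores at each of the (hypoglycemic) glycemic plateaus", a shift in the detection threshold, and the hormone responses at the second clamp. Improvement is judged "compared to their baseline and/or compared to the placebo-treated control group". Section 9.11.2 describes baseline comparisons, but only for the secondary CGM variable.

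**The concern.** Two things are left open.

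- **Use of clamp 1 in the between-arm test.** The wording fits a test of clamp 2 alone or a test of change from clamp 1 (the arm-by-clamp term of a repeated-measures ANOVA). Neither is the most precise use of a baseline unless the between-clamp correlation is low or high. With 7 per arm there is little precision to spare, and an unspecified choice could be made after the data are seen.
- **The comparator.** A within-arm change has no control. Regression toward the mean is possible in people enrolled for impaired awareness. All participants also keep a hypoglycemia log and repeat the same questionnaires and clamp. Any resulting shift would be common to all arms, and under the and/or wording it could be read as a drug effect. Only the placebo comparison removes it.

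**Working it through.** **Inputs from Section 10.** N = 21, g = 3 arms of 7, significance level 5%, power at least 80%.

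**Assumptions, not in the documents.** Two-sided tests, normal data, equal SD at both clamps, no dropout, correlation r between clamps, effect in SD units.

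**1. The plan's own figure.** The 80% power for 21 patients cannot be reproduced, because no effect size or SD is given. Solving backwards, 7 per arm with a pooled three-arm error (18 df) gives 80% power for a clamp-2-only difference of 1.58 SD.

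**2. Precision.** Variance of one dose minus placebo, in units of 2σ²/7:

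- clamp 2 only: 1
- change score: 2(1 − r)
- three-arm ANCOVA: (1 − r²)(1 + 1/(N − g − 2)) = (1 − r²)(1 + 1/16) = 1.0625(1 − r²)

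ANCOVA beats clamp-2-only when r > √(1 − 1/1.0625) = 0.243. It beats change when 1.0625(1 + r) < 2, that is r < 0.882. Allowing for 17 rather than 18 error df in the critical value, the range is about 0.26 to 0.87.

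| r | clamp 2 only | change | ANCOVA |
|---|---|---|---|
| 0 | 1 | 2.00 | 1.06 |
| 0.3 | 1 | 1.40 | 0.97 |
| 0.5 | 1 | 1.00 | 0.80 |
| 0.7 | 1 | 0.60 | 0.54 |
| 0.9 | 1 | 0.20 | 0.20 |

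**3. Power.** Simulated, one dose against placebo, effect 1.2 SD:

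| r | clamp 2 only | change | ANCOVA |
|---|---|---|---|
| 0 | 57% | 32% | 54% |
| 0.3 | 56% | 44% | 58% |
| 0.5 | 57% | 57% | 66% |
| 0.7 | 56% | 79% | 82% |

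Type I error is 5.0 to 5.1% for all three. The gain over the better of the first two at r = 0.3/0.5/0.7 is about 1/9/4 points at 1.2 SD. It is 0/2/2 at 0.5 SD, 1/6/4 at 0.8 SD, 1/8/1 at 1.58 SD and 0/3/0 at 2.0 SD. At r = 0.5 the effect detectable with 80% power falls from 1.58 to 1.42 SD.

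**4. Where the assumptions fail.** With a clamp-2 to clamp-1 SD ratio s, the change variance is s² + 1 − 2rs and the ANCOVA variance is 1.0625 s²(1 − r²). At s = 1.25, change is more precise for r of about 0.60 to 0.91; at s = 1.5, for about 0.44 to 0.81.

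A floor is plausible. Section 9.10 says "symptoms may not manifest in hypoglycemia unaware patients until glucose levels reach 45mg/dl", and Section 2 says the glucagon response "either becomes significantly attenuated or is completely absent in diabetic patients". Simulated power, clamp-2-only/change/ANCOVA, at a 1.2 SD effect:

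| clamp-1 values at floor | r = 0.3 | r = 0.5 | r = 0.7 |
|---|---|---|---|
| 50% | 46/42/46% | 47/51/52% | 46/67/64% |
| 70% | 36/34/35% | 36/40/38% | 35/50/45% |

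**5. The and/or route.** No drug effect, r = 0.5, one variable, one plateau. A trial counts as positive if either carvedilol arm shows a significant improvement on a paired t-test, or either dose is significantly better than placebo by ANCOVA.

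| drift shared by all arms (assumed) | and/or route | placebo contrasts only |
|---|---|---|
| 0 | 8% | about 4.5% |
| 0.3 SD | 21% | about 4.5% |
| 0.5 SD | 37% | about 4.5% |
| 0.8 SD | 68% | about 4.5% |

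**The case against.** A repeated-measures ANOVA is within the plan's wording, and its arm-by-clamp term already brings in clamp 1 as a change score with correct type I error. Preferring ANCOVA is then a choice of efficiency, and the gain depends on a correlation and an effect size that the documents do not give. That stands in part: the gain is often small, 9 points is near the best case, and change scores do better if clamp-2 spread is larger or many values sit at a floor. But the plan permits that test without committing to it, and change scores lose to clamp-2-only below r = 0.5.

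The drift sizes are assumed, and Section 10 names no paired tests. That is also true. The and/or wording still admits the within-arm comparison, and some inflation remains with no drift at all.

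A reader might infer more than the documents support:

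- *The planned between-arm tests are invalid.* They are not. Clamp-2-only, change and ANCOVA each hold 5% for a single prespecified contrast.
- *The plan means to test a group effect averaged over both clamps.* Such a test would have 21 to 26% power at 1.2 SD and r = 0.3 to 0.7. But Section 9.10 treats clamp 1 as baseline and Section 9.11.1 looks at the second clamp, so a fair reading excludes it.
- *The and/or route gives a false claim in 16% of trials without drift.* That rate counts significant worsening. Section 9.11.1 seeks improvement, for which the rate is 8%.

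**Conclusion.** The concern holds, at moderate weight. The omission in Section 10 and the Study Summary is certain; its cost is one of precision and is modest, about 0 to 9 points of power. ANCOVA's advantage over both alternatives for r of about 0.24 to 0.88 requires normal data, equal SDs, no floor and a single three-arm model. It is not a general superiority, and at 7 per arm even 1.42 SD remains a large detectable effect.

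The and/or comparator is the more serious part because it concerns validity. The chance of a spurious improvement is about 8% without drift and rises steeply with any shared shift, while the placebo contrasts stay near 4.5%. How large such a shift would be cannot be learned from the documents.

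**What to change.** **Section 10 and Study Summary, primary variables.** Replace the generic sentence with text such as:

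> For each primary variable at each hypoglycemic plateau (65, 55 and 45 mg/dl), the treatment effect is the difference between each carvedilol arm and placebo in the clamp-2 value. It is estimated from one ANCOVA of all three arms, with the same participant's clamp-1 value at that plateau as covariate.

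An equivalent mixed model is acceptable if it is reported per plateau. Keep all arms in one model: separate 14-patient ANCOVAs narrow the favorable range to r of about 0.30 to 0.82. The ANOVA sentence can stay for the secondary variable.

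**Section 9.11.1.** Make the comparison with placebo the primary test and the within-arm change from baseline descriptive.

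**Cost.** No new data or visits, and SAS is already named. One error degree of freedom is used (18 to 17). About 3 points of power are lost if r is near 0 (57% to 54% at 1.2 SD). A few points, up to about 5, are lost to change scores with larger clamp-2 spread or a heavy floor.

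Multiplicity across plateaus, doses and variables, and the analysis of the threshold shift in Section 9.11.1, are separate matters that this change does not settle.

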4.3 Number of Subjects

21 Type 1 diabetic patients with hypoglycemia unawareness will be recruited for the study. The 21 T1DM patients will be randomly allocated to one of the following treatments: 1) placebo (N=7), 2) 2.5mg carvedilol twice daily (N=7) or 3) 3.125mg carvedilol twice daily (N=7). Placebo will be taken twice daily.

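### If the repeated-measures ANOVA option is used in its classical form, one missing plateau value drops a participant from that variable's whole test; a mixed model on all observed values avoids this

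*Combined protocol and SAP*

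**What the plan says.** Section 10 gives one sentence on method: "one- or two-way analysis of variance (ANOVA) for independent or repeated measures as appropriate", followed by unspecified post-hoc tests. The Study Summary has the same wording. On software it says "Analyses will be performed using the GraphPad Prism" or SAS, with no procedure named. Power is set through a Type II error "of no more than 20% for a given test" and alpha of 5%, with 7 per arm (section 4.3). No effect size, SD, analysis population, dropout allowance or missing-value rule is given.

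The data are repeated within person. Section 9.10 describes "gradually lowering plasma glucose levels in three steps from 90-65-55-45 mg/dl", with samples and questionnaires before the clamp and then: "At each glycemic step, plasma hormones (glucagon, catecholamines, insulin, cortisol, growth hormone, pancreatic polypeptide) will be evaluated". The Edinburgh questionnaire is also completed at each plateau, and the second clamp is identical to the first. Section 9.11.1 makes the first primary assessment "improvements in the hypoglycemia symptom scores at each of the (hypoglycemic) glycemic plateaus", judged against the participant's own baseline and/or against placebo.

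**The concern.** Classical repeated-measures ANOVA needs a full set of values for every participant analysed. A spoiled 65 mg/dl sample would therefore discard that participant's valid 55 and 45 mg/dl values for the same variable. With 7 per arm, each discarded participant is 1/7 = 14% of an arm.

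Nothing in the plan prevents this. Because the choice of ANOVA is left to what is appropriate, it could also be made after it is known which values are missing. The trial would then have collected and paid for data that its primary test does not use.

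**Working it through.** **The plan's own figure.** Seven per arm for 80% power cannot be reproduced, because no effect size or SD is stated. Solving backwards with two-sided alpha 0.05 (sidedness is not stated):

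- Normal approximation: (1.96 + 0.84) × √(2/7) = 1.50 SD.
- Exact noncentral t at 7 v 7 (12 degrees of freedom): 1.63 SD.

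The 1.63 SD effect is held fixed below, so that complete data give 0.80. At that effect, 6 per arm gives 0.72, 5 per arm gives 0.62, and 7 v 6 gives 0.76.

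**Values per participant and variable.** These follow from section 9.10. One clamp has 3 hypoglycemic plateaus, or 4 values with the pre-clamp value. Two clamps have 6 or 8. The plan does not say which set enters the model.

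**Completeness.** With a fraction q of values lost independently and at random, P(complete) = (1 − q)^k. At an assumed q = 3%:

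| k | P(complete) | Expected dropped of 21 |
|---|---|---|
| 3 | 0.913 | 1.8 |
| 4 | 0.885 | 2.4 |
| 6 | 0.833 | 3.5 |
| 8 | 0.784 | 4.5 |

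The chance that all 21 are complete is P(complete)^21: 8% for 4 values and under 1% for 8.

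**Power after deletion.** Completers per arm are Binomial(7, P), and exact t power is averaged over both arms. The comparison uses each plateau's own data, which needs one value (k = 1) for a second-clamp analysis and two (k = 2) when both clamps are used.

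| Loss per value | One clamp: own data | 3 values | 4 values | Both clamps: own data | 6 values | 8 values |
|---|---|---|---|---|---|---|
| 1% | 0.79 | 0.78 | 0.78 | 0.79 | 0.77 | 0.75 |
| 3% | 0.78 | 0.75 | 0.73 | 0.77 | 0.69 | 0.65 |
| 5% | 0.77 | 0.71 | 0.68 | 0.74 | 0.61 | 0.55 |

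**Cross-checks.**

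- Simulation of the one-clamp case at 3% loss gave 0.74 to 0.75 against 0.79, within a point of the table.
- Simulated ANCOVA at 45 mg/dl used 20,000 runs, an effect of 1.38 SD and between-clamp correlation 0.6. Complete-data power was 0.80. For 6 / 8 values against own data it gave 0.76 / 0.75 against 0.79 at 1% loss, 0.68 / 0.64 against 0.77 at 3%, and 0.59 / 0.52 against 0.74 at 5%.
- Across the exact and ANCOVA calculations, the both-clamp gap at 5% loss runs from 0.74 − 0.61 = 13 points to 0.74 − 0.52 = 22 points.

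**Does a mixed model recover the loss?** A simulation of 1,500 runs per setting compared complete-case repeated-measures ANOVA with a REML random-intercept model on all observed values, at within-person correlation 0.5 or 0.7 and 2% to 5% loss. The mixed model gave 0.78 to 0.81 in every completed setting, against 0.79 to 0.81 with nothing lost. Complete-case ANOVA at 3% loss gave 0.72 to 0.73 (4 values) and 0.64 to 0.65 (8 values). This simulation assumed the same effect at every value, which is simpler than a pre/post contrast at one plateau. The setting with 8 values, correlation 0.7 and 5% loss did not finish.

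**The case against.** The strongest objection is that the plan does not commit to the method criticised. Its wording equally allows a one-way independent ANOVA at each plateau, which loses only the affected plateau and suits a primary assessment defined plateau by plateau. SAS, already named, can fit a mixed model. This stands: a reader might infer that the plan will delete participants, but the text neither commits to that nor rules it out.

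The second objection concerns size. A two-way ANOVA of arm by plateau holds only the second clamp's 3 or 4 values, and there the gap at 3% loss is about 4 to 5 points. This also stands. The larger losses need both clamps in the model, and the loss rate is assumed throughout.

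Three further inferences are not supported:

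- That one failed assay removes a participant from every primary result. It affects that variable's model only, unless the whole draw is lost.
- That deletion removes the most responsive participants, for example through an unfinished 45 mg/dl step. The documents describe no step being cut short and no pattern of missing values.
- That differing patient sets between hormones are peculiar to ANOVA. A failed assay changes who contributes under a mixed model too.

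What remains is that the repeated-measures option has an avoidable cost, the plan leaves it open, and a better method is available in software already named.

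**Conclusion.** The point holds as a conditional one. Under the classical repeated-measures option, a single missing value discards valid data for that variable. A reader might conclude that a few percent of lost samples costs much of the power. That fits only models holding both clamps at about 3% to 5% loss. With the second clamp alone, or at 1% loss, the cost is small to moderate.

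The figures assume independent random loss and a true effect that gives exactly 80% power at 7 v 7. At a smaller effect, power is low before anything is lost: 0.41 at 1.0 SD. The change is worth making before analysis, but the finding does not invalidate the design.

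**What to change.** In section 10 and the Study Summary, replace repeated-measures ANOVA with a linear mixed model fitted by REML in SAS to all observed values, and choose one of two forms in advance:

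1. **Both clamps as outcomes.** Arm, clamp, plateau and their interactions, with a participant-level covariance. The treatment effect is the arm-by-clamp contrast at each plateau.
2. **Second clamp as outcome.** Arm, plateau, arm-by-plateau, and the first-clamp value at the same plateau as covariate. A missing first-clamp value then loses that plateau's row, but not the participant's other plateaus.

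A model with arm and plateau only is not enough. It would either pool pre- and post-treatment values or give up the baseline adjustment.

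Use Kenward-Roger degrees of freedom. Name a simpler covariance in case the unstructured one does not converge. That is a real prospect with 21 participants: an unstructured matrix has k(k + 1)/2 parameters, so 6 for 3 values, 21 for 6 and 36 for 8. Make plateau-by-plateau available-case ANCOVA the final fallback. State that no participant is dropped because a value at another plateau is missing.

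The cost is SAP wording and a standard procedure, with no new patients or measurements. The price is a missing-at-random assumption and a stated convergence fallback. Participants who never have a second clamp are not recovered.
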